### Sample Characteristics:

Among enrolled families at baseline, parents were on average 43.7 years of age ( $SD = 6.7$ ) and their teens were 16 or 17 years of age ( $M = 16.4$ ,  $SD = 0.5$ ). Mothers comprised 84.7% of the parents and slightly more than half (55.3%) of the teens were females. Household size ranged from two to 12 ( $M = 4.5$ ,  $SD = 1.6$ ). About one-tenth (9.5%) of the teens were Hispanic/Latino.

Teens reported the following race/ethnicities: 72.5% White, 1.9% Asian, 11.7% African American, 1.0% Native American, 8.3% Multiracial, 2.7% some other race, and 1.9% unreported. No significant differences were found between the experimental and control conditions on demographic characteristics at baseline.

### **Exposure to Treatment**

Concerns about Recruitment: Because the intervention is available online, families could complete the intervention in their own homes, at a time convenient for them. Thus, some of the typical barriers to participation were removed. Despite these barrier reductions, only half (49.5%) of the families assigned to the intervention condition completed the program materials on teen alcohol use and less than half (42.7%) completed the materials on romantic/sexual relationships.

There are many reasons for prevention strategies to fall short of this total “inoculation” of the general population. First, families whose teens are perceived as “doing fine” or “not in need of any prevention” are difficult to engage in prevention. Second, parents sometimes believe that it is important not to prevent risky behaviors of teens like drinking and sexual activity but rather to teach teens how to engage in these behaviors while minimizing risks; they may not view a prevention program as aligned with their parental values. Third, families with teens who are already engaged in heavy alcohol consumption and/or engaged in risky sexual behaviors need a more intensive treatment intervention. Fortunately, there does not need to be total saturation of the general population for community-level perspectives to change. Nonetheless, an efficacious intervention that reaches even a sizeable proportion of the general population does potentially provide a resource to a sizeable number of families. Furthermore, parents of older teens do express a desire for some support and help in managing these “adult” behaviors.

### **Analyses:**

Descriptive analyses were conducted first to describe rates and mean scores of outcomes overall and by condition across three assessments to check the randomization.

Selection model: Because families chose how much of the intervention to which they were exposed, we conducted a probit analysis predicting whether or not a family completed the alcohol or relationship component from baseline measures. Based on this analysis, an instrumental variable, inverse Mills’ ratio (IMR) representing the underlying selection processes was included as a covariate in our primary dosage analyses (Heckman, 1979). The IMR (non-selection hazard) was calculated in Stata using the two-step procedure described in Heckman (1979). When the IMR is significant in a model, this indicates that the predicted probability of completing the component is associated with the outcome. That is, the same factors that predispose families to complete (or not complete) the component are related to the outcomes. In models where dosage is significant, this indicates that even accounting for factors that are related to completing the program, that dosage is still related to outcomes.

Conducting analyses in SPSS 21, dichotomous outcomes were examined using multiple logistic regression, while continuous outcomes were examined using multiple linear regression. Listwise deletion was used for missing cases. For all regression analyses, the baseline value of the outcome variable, teen gender, teen age, and teen ethnicity, an inverse Mills’ ratio and intervention condition, were covariates to determine whether dosage predicted the outcome for a specific follow-up period (i.e., 6, 12 18 months).

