### **Assessment of Efficacy-Overview:**

Results from the Smart Choices 4 Teens program indicate efficacy for prevention of alcohol use and alcohol-related problem behaviors for older teens when parents and teens, with greater exposure to the program content producing better outcomes, when controlling for baseline rates and selection bias. The intervention also showed efficacy for parent–teen communication, especially around conversations related to social host laws. Further parents and teens engaged in the program were less likely to discuss ways that teens could drink “safely,” and thus not providing a message that teens could drink if they drank safely. Of particular importance is that the dosage effects were noted across different alcohol involvement indicators and some of these impacts persisted at the 12-month follow-up period, showing that the program may have sustained effects.

For the relationships/sexual behaviors component of the intervention, the data support the efficacy of the Smart Choices 4 Teens intervention in increasing adolescent and parent communications about sexual relationships (eg, frequency) and to increase parental guidance (eg, dating rules) when controlling for baseline rates and selection bias. There was some support that the intervention had a main effect on frequency of communication and dating rules set for the adolescents, even after controlling for other adolescent characteristics that were also significant predictors of adolescents’ reports of sexual communication with their parents, including developmental changes over time, as well as adolescent gender, sexual minority status, and sexual experience.

There were indications that the intervention had impact on sexual communication over time, irrespective of the gender of the adolescent. When accounting for the possible interaction between the time of administration, gender of the adolescent, and exposure to the intervention, demonstrated an impact on the parent-teen sexual communication outcome. The intervention increased parent-teen communications regarding increased dating rules, indicating greater parental monitoring of teen relationships. There was no indication of an interaction effect between gender and intervention exposure on dating rules. Participating in the intervention increased the dating rules for all participants and was durable across time.

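### The inverse Mills' ratio, as described, adjusts only for measured predictors of completion, so the alcohol efficacy statement claims more than the dosage analysis supports

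*Combined protocol and SAP*

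**What the plan says.** The Analyses section (Selection model) describes the first step: "we conducted a probit analysis predicting whether or not a family completed the alcohol or relationship component from baseline measures". The resulting ratio is labelled an instrumental variable and was "representing the underlying selection processes was included as a covariate in our primary dosage analyses". On its construction the text says only: "The IMR (non-selection hazard) was calculated in Stata using the two-step procedure described in" the cited paper on sample selection. No formula, predictor list or coding for non-completers and controls is given. When the ratio is significant, "this indicates that the predicted probability of completing the component is associated with the outcome". A significant dosage term is read as an association that remains after factors related to completion are accounted for.

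The outcome models are linear or logistic. For all regression analyses, the baseline outcome, teen gender, age, ethnicity, the ratio and intervention condition "were covariates to determine whether dosage predicted the outcome for a specific follow-up period". Results by condition are mentioned only as descriptive statistics, to check the randomisation.

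Assessment of Efficacy-Overview claims efficacy for alcohol outcomes, "with greater exposure to the program content producing better outcomes, when controlling for baseline rates and selection bias". It adds: "Of particular importance is that the dosage effects were noted across different alcohol involvement indicators". A main effect is named only for two relationship outcomes: "There was some support that the intervention had a main effect on frequency of communication and dating rules set for the adolescents".

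**The concern.** A covariate computed from baseline measures carries no information beyond those measures. It can balance completers and non-completers on what was recorded at baseline, and that is useful. It cannot deal with an unrecorded characteristic that makes a family both more likely to finish and more (or less) likely to have a teen who drinks.

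An instrument would have to shift exposure without otherwise affecting the outcome. Random assignment is the natural candidate here, but the models use it only as a covariate.

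The overview goes beyond the Analyses section in two ways: a remaining association becomes exposure *producing* outcomes, and adjustment for factors related to completion becomes control of *selection bias* in general. What is at stake is the alcohol conclusion of a randomised trial, which as written leans on a contrast that was not randomised.

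**Working it through.** **What the dosage coefficient compares.** Exposure to Treatment gives completion in the intervention arm as 49.5% (alcohol) and 42.7% (relationship). Assume that controls had no program access, which fits the description of the control condition. Dosage then varies only inside the intervention arm. With condition in the model, its coefficient contrasts completers with non-completers in that arm, a comparison that randomisation does not protect.

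**No planned figure to reproduce.** The documents give no alpha, power or effect size for this analysis. The size of the problem can only be illustrated.

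**Simulation inputs.**
- From the documents: 411 families; 76.6% teen follow-up at 6 months (315/411), taken as missing at random; 49.5% completion.
- Inferred: 206 families in the intervention arm, since 102/206 = 49.5% and 88/206 = 42.7%. The arm size is not stated.
- Assumed: latent completion = −0.2 × baseline outcome + 0.2 × gender + 0.5 × m + N(0,1). Outcome = 0.5 × baseline + 0.1 × gender + b × m + N(0,1). Here m is a baseline measure in the probit but not in the outcome model. Rho is the correlation of the two error terms. The true dosage effect is 0 and a lower outcome is better.
- Ratio = pdf/(1 − cdf) of the probit index, entered as a covariate beside dosage and condition, with its predicted value also used for controls.
- There were 2,000 trials per scenario. Units are residual SD. Total SD is about 1.12 when b = 0 and 1.16 when b = −0.3, so 0.30 residual SD is about 0.30/1.12 = 0.27 total SD.

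| Scenario | Dosage coefficient, no ratio | With ratio | False significance with ratio |
|---|---|---|---|
| rho −0.1, b = 0 | −0.14 | −0.15 | 15% |
| rho −0.2, b = 0 | −0.28 | −0.30 | 44–46% |
| rho +0.1, b = 0 | +0.14 | +0.15 | 15% |
| rho +0.2, b = 0 | +0.29 | +0.30 | 44–46% |
| measured selection only (rho 0, b = −0.3) | −0.22 | −0.01 | 5% (24% without it) |
| both, rho −0.2 | −0.50 | −0.31 | |
| both, rho +0.2 | +0.07 | +0.29 | |

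The ratio removes measured selection and leaves unmeasured selection in place. Negative rho gives false benefit and positive rho gives false harm. With a logistic outcome at an assumed 30% prevalence, the odds ratio with the ratio in the model was 0.77 / 0.59 at rho −0.1 / −0.2 and 1.30 / 1.69 at +0.1 / +0.2. The comparison by randomised condition, without dosage or ratio, stayed within 0.01 of 0 (SD or log-odds), with 4.1–5.8% rejection.

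**The condition coefficient in the same model.** Its meaning depends on how the ratio was coded for controls, which the text does not say. At rho −0.2 it was about +0.15 with the predicted ratio given to controls and about +0.01 with the ratio set to 0 for them. With the ratio set to 0 and m affecting the outcome, it was about +0.70. The true effect of assignment was 0 throughout. So this coefficient is not the effect of assignment, and the text does not allow it to be described more precisely.

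**Precision of the by-condition comparison** (315 teens, equal arms, no covariate gain, total SD). The standard error is √(4/315) = 0.113. The 95% half-width is 1.96 × 0.113 = 0.22 SD. The effect detectable at 80% power is 2.80 × 0.113 = 0.32 SD. If only completers respond, that needs 0.316/0.495 = 0.64 SD (alcohol) or 0.316/0.427 = 0.74 SD (relationship) among them.

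**The case against.** The strongest reply is that the Heckman two-step procedure is meant for unmeasured selection. This stands in part. With a signed, completer-specific hazard, joint normality and a valid excluded predictor, the simulated bias fell to between 0.00 and +0.02 SD, although the standard error rose from 0.17 to about 0.43. When the excluded predictor did affect the outcome, the bias was −1.50 SD. The text describes neither such a term nor such a predictor, and it reads the ratio as predicted completion. The formula and predictor list therefore decide what was adjusted for, and both need to be stated.

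Second, the Analyses section itself reads dosage as an association, so the overstatement lies mainly in two phrases of the overview. The alcohol sentence there also seems to have lost some words and may assert efficacy and, separately, a dosage gradient. That is fair, and it is why the point is that the conclusion *leans on* dosage as written, not that nothing else could support it.

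Third, a reader might infer that no by-condition alcohol analysis was done. The documents do not show this. The main-effect sentence mentions sexual minority status and sexual experience, which are not among the covariates in the Analyses section, so other models evidently exist, and details are deferred to an online report and publications. For the same reason it cannot be said that the main-effect statements on communication and dating rules are free of the problem, or that they share it: the text does not say whether those models contained dosage.

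Fourth, the reasons for non-completion in Exposure to Treatment might suggest bias in favour of the program. They are general discussion and point both ways. Families whose teens seem to be doing fine would bias against the program if they drop out. The parental-values reason could bias towards it. Heavy drinking is largely captured by baseline values.

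**Conclusion.** The point holds as a mismatch between analysis and claim, and should be fixed. As described, the ratio is not an instrument and adjusts for measured selection only, so the overview's causal wording and its reference to selection bias go beyond the dosage analysis. This rests on the text's own description of the ratio and on controls having had no program access.

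The illustrative size is about 0.15 residual SD at |rho| = 0.1 and 0.30 at |rho| = 0.2, in either direction. Rho is assumed, and these figures do not estimate this trial's bias. A reader might infer that the dosage effects are false or that the program does not reduce drinking. The documents support neither reading.

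**What to change.** 1. Report the comparison by randomised condition at 6, 12 and 18 months for each alcohol and relationship outcome, with the baseline covariates already listed, without dosage or the ratio, and with confidence intervals. Rest the efficacy conclusions on it, and label dosage results as secondary and observational.
2. In Assessment of Efficacy-Overview, for dosage results, replace *producing* with *associated with* and *selection bias* with *measured baseline predictors of completion*. Say which statements come from by-condition models.
3. In Analyses, delete the description of the ratio as an instrumental variable. Give its formula, its coding for non-completers and controls, and the probit predictors. Add: *Unmeasured selection may remain, in either direction. With dosage in the model, the condition coefficient is not the effect of assignment.* Do not state that this coefficient compares assigned non-completers with controls, because that depends on the coding.
4. Optional: two-stage least squares for one binary definition of completion, with assignment as the instrument, as a secondary analysis with sensitivity analyses of the exclusion assumption. Its interval is 1/0.495 = 2.02 (alcohol) or 1/0.427 = 2.34 (relationship) times as wide, a half-width of about 0.45 or 0.52 SD. If assigned non-completers have an effect d and completers have none, it is off by d(1 − p)/p, where p is the completion proportion. At d = 0.1 that is 0.10 SD (alcohol) or 0.13 SD (relationship).

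Items 1 to 3 cost a little analyst time and some rewording. The dosage statement becomes less favourable. Power by condition is limited, so a null result would not rule out a moderate benefit among completers. None of this repairs missing follow-up.

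### The dosage models for Yes/No alcohol use and for communication outcomes leave out baseline drinking level, which was collected, and the inverse Mills' ratio covers the gap only if its unreported probit is flexible in drinking level

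*Combined protocol and SAP*

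**What the plan says.** All references are to the combined protocol and SAP.

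- **Exposure is self-selected.** The Analyses section gives this as the reason for a selection model: "Because families chose how much of the intervention to which they were exposed". Under Exposure to Treatment, "only half (49.5%) of the families assigned to the intervention condition completed the program materials on teen alcohol use"; for the relationship component the figure is 42.7%.
- **Adjustment.** The dosage regressions hold "the baseline value of the outcome variable, teen gender, teen age, and teen ethnicity", together with an IMR and randomized condition. The IMR comes from a probit of component completion on baseline measures. Neither the measures nor their functional form is listed.
- **Reasons for incomplete reach.** Exposure to Treatment discusses why prevention programs in general miss families. Those whose teens seem to be doing well "are difficult to engage in prevention". Some parents would rather teach lower-risk drinking than prevent it. Families whose teens already drink heavily "need a more intensive treatment intervention". No completion rate by baseline drinking is reported.
- **What was collected.** The Measures text describes Yes/No use, frequency, usual quantity and drunkenness.
- **What rests on the models.** Assessment of Efficacy-Overview claims better alcohol outcomes with greater exposure, after control for baseline rates and selection bias.

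**The concern.** If completion is lowest among both the lowest-risk and the heaviest-drinking teens, then among baseline drinkers the completers are lighter drinkers than the non-completers. A Yes/No baseline treats the two groups as alike. Their later difference in drinking would then load on the dosage term even if the program did nothing.

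The IMR need not repair this. It is a monotone function of one fitted index. It can represent completion that is low at both ends of drinking level only if the index itself bends with drinking level, that is, if the probit has categories or a non-linear term. The plan describes none.

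The same gap exists for communication outcomes, whose own baseline is not a drinking measure. At stake is the efficacy statement, which relies on selection having been controlled.

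**Working it through.** The documents give no figure to reproduce for this point, and no alpha, power or allocation ratio. The checks assume two-sided 0.05, 1:1 allocation and no program effect.

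**1. Any use, by hand.** Assumed baseline shares: 60% none, 25% light, 15% heavy. Assumed later use: 12%, 55%, 85%. Assumed completion: 45%, 75%, 25%.

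- Overall completion = 0.60×0.45 + 0.25×0.75 + 0.15×0.25 = 0.270 + 0.1875 + 0.0375 = 49.5%, which matches the reported rate.
- Completers among baseline drinkers: light 0.1875, heavy 0.0375. Later use = (0.1875×0.55 + 0.0375×0.85)/0.225 = 0.135/0.225 = 60.0%.
- Non-completers among baseline drinkers: light 0.0625, heavy 0.1125. Later use = (0.0625×0.55 + 0.1125×0.85)/0.175 = 0.130/0.175 = 74.3%.
- Odds ratio among baseline drinkers = (0.600/0.400)/(0.743/0.257) = 1.50/2.89 = 0.52. Among baseline non-drinkers it is 1.

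A Yes/No baseline does not remove this difference.

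**2. Any use, fitted model.** Logistic regression on dosage, condition and Yes/No baseline use, with the IMR as stated, for the pattern above and two milder ones (40/70/40 and 50/60/30, with overall completion 47.5% and 49.5%). If the probit carries use but no drinking level, its IMR adds almost nothing beyond baseline use.

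| Adjustment | Dosage OR | False positives |
|---|---|---|
| Probit without drinking level | 0.68-0.81 | about 6-15% |
| Probit with use and linear frequency | 0.84-1.00 | about 3-8% |
| None/light/heavy in the outcome model | about 1.0 | about 4-7% |

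The second row depends on how frequency is distributed within the light and heavy groups. With one value per group, use plus frequency identifies all three groups and the OR is 1.00-1.02. With a spread on the raw 0-5 score it is 0.92-0.96. With a long right tail, as the recoded counts may have, it is 0.84-0.90.

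**3. Other outcomes and selection shapes.** Here baseline drinking is a standard normal variable, and completion either changes steadily with it or peaks in the middle. Large-sample bias; error rates at 411 enrolled with 75.7% followed up.

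| Outcome | Setting | Bias | Type I error |
|---|---|---|---|
| Any use | Steady selection, drinking not in probit | -0.17 to -0.35 log-OR (OR 0.84 to 0.70) | 8-16% |
| Any use | Steady selection, drinking linear in probit | about 0 | 4-7% |
| Any use | Mid-peaked selection | -0.06 to +0.12 log-OR (OR 0.94 to 1.13) | 4-6% |
| Communication | Steady selection, drinking not in probit | -0.09 to -0.22 | 8-37% |
| Communication | Mid-peaked selection, curved drinking effect, no squared term in probit | -0.09 to -0.14 | 8-15% |
| Communication | Mid-peaked selection, linear drinking effect | 0 | 3-5% |
| Frequency | Linear in its own baseline, either shape | 0.00 to 0.01 | 4-6% |
| Frequency | Curved in its own baseline, mid-peaked selection, no squared term in probit | -0.13 to -0.21 (residual SD 0.8) | 15-34% |

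Adding drinking level and its square to the outcome model brings the bias to at most 0.012 for the continuous outcomes and 0.04 log-OR for any use, with type I error of 4-7%.

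**The case against.** The strongest reply is that the problem depends on two things the documents do not say.

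- **Completion pattern.** A reader might infer from Exposure to Treatment that low-risk and high-risk families in this trial were seen not to complete. The text does not report that. It discusses prevention programs in general, and the remark on heavy drinkers concerns their need for more intensive help, not observed dropout. This part of the reply stands: two-ended selection is plausible, not documented.
- **Probit.** A reader might also infer that baseline drinking entered the probit linearly or not at all. The plan says neither. Drinking could already be there, even as categories. This also stands, but it means the control of selection cannot be verified from the plan.

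Other points stand in part. The frequency, quantity and drunkenness models already hold their own baseline level, so they are affected only if that relation is non-linear. With use and linear frequency in the probit, the inflation of false positives for any use is small. The efficacy overview mentions sexual experience among the characteristics controlled in the relationship analyses, although it does not say that the dosage models contain it. The safe-drinking scale measures how often the topic was discussed and is itself an outcome, so it is at best a proxy for parental values.

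None of this explains leaving a collected measure of drinking level out of the Yes/No use and communication models.

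**Conclusion.** The point holds as a gap in adjustment, not as demonstrated confounding. For Yes/No use and for communication outcomes, the listed covariates contain no baseline drinking level, and the IMR fills the gap only under a probit specification that is not reported. For any use, with no program effect, the spurious dosage OR is about 0.7-0.8 if the probit omits drinking level and about 0.85-1.0 if it holds use plus linear frequency. Every completion pattern, risk and frequency distribution behind these figures is assumed; only the overall completion rate and the sample counts come from the documents.

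Two stronger conclusions are tempting. One is that the reported dosage effects are artefacts of selection. The other is that the bias must favor the program. The documents support neither: no completion by drinking level is given, and for any use under mid-peaked selection the bias ran in both directions.

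**What to change.** 1. Form baseline drinking categories (none, light, heavy) from the frequency, quantity and drunkenness items. Add them to the dosage outcome models for Yes/No use and communication, and to the probit.
2. List the probit predictors and their functional form.
3. Report completion of each component by baseline drinking category, so that the selection pattern can be seen.
4. In Assessment of Efficacy-Overview, make the statement about controlling for selection bias conditional on the dosage results holding after step 1.
5. Check the frequency, quantity and drunkenness models for non-linearity in their own baseline.
6. Confirm that baseline sexual experience is a covariate in the relationship dosage models. The baseline safe-drinking communication scale may be added as a proxy for parental values.

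The cost is two or three extra terms per model and a re-run of existing analyses on data already held.
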